The null hypothesis for the study is that there is no treatment difference (in mean S-K levels Days 8-29) between each ZS dose (high to low) versus placebo control. The alternative hypothesis is that ZS is more effective than the placebo control in maintaining mean 28-day randomized treatment study phase Day 8-29 serum potassium levels (3.5-5.0 mmol/L, inclusive) among hyperkalemic patients in whom normokalemia is established during the open-label initial phase.

All efficacy analyses will be based on the S-K values obtained from the Central Laboratory. If Central Laboratory data are missing, they will be replaced by i-STAT values adjusted with the mean paired difference between i-STAT and S-K values collected at the same visit. More details on how to handle dropouts and missing data will be provided in the SAP.

The primary endpoint in the study will be the model-based least squares means (LSMEANS) of all available S-K values during the 28-day randomized treatment study phase Days 8-29. A log transformation will be applied to the S-K levels, since historical data shows that S-K measurements follows a log-normal distribution, and also to stabilize the variance. A longitudinal model (SAS PROC MIXED) will then be used to simultaneously compare each active dose (high to low) versus placebo control for the 28-day randomized treatment study phase to estimate the least squares means Day 8-29 values. The model will include all S-K data collected at the scheduled visits between Day 8-29 as response variables, with baseline covariates for the open-label initial phase eGFR, the open-label initial phase S-K values, the 28day randomized treatment study phase S-K values as well as age (<55, 55-64, >64 years), country and baseline binary indicators for RAAS inhibitors, chronic kidney disease, heart failure, and diabetes mellitus as fixed effects terms and patients are random effect term. In addition, the primary efficacy endpoint and the secondary efficacy endpoint of the proportion of patients who remain normokalemic (as defined by S-K between 3.5-5.0 mmol/L, inclusive) at the end of the 28-day randomized treatment study phase will be evaluated for the subgroups (i.e., CKD DM, HF and those on RAAS inhibitors). More details will be described in the SAP.

Secondary efficacy endpoints will include:

- The proportion of patients who remain normokalemic (as defined by S-K between 3.5-5.0 mmol/L, inclusive) at the end of the 28-day randomized treatment study phase and during the 28-day randomized treatment study phase.
- The number of days patients remain normokalemic during the 28-day randomized treatment study phase.
- The mean change and mean percent change in S-K levels evaluated relative to both baselines.
- The time to hyperkalemia (defined as $S-K \ge 5.1 \text{ mmol/L}$).
- The mean change in S-Aldo and P-Renin levels.

Safety endpoints will include adverse events (AEs), serious AEs (SAEs), vital signs, clinical laboratory evaluations, physical examinations, ECGs, and other serum electrolytes (specifically, serum calcium [S-Ca], serum magnesium [S-Mg], serum sodium [S-Na], serum phosphate [S-PO₄], serum bicarbonate [S-HCO₃], and blood urea nitrogen [BUN]).

The confirmed i-STAT potassium value on Study Day 2 or Day 3 of the open-label initial phase will be used to established the patient's eligibility into the 28-day randomized treatment study phase, however central laboratory S-K values will be used for all analyses.

Sensitivity analyses will be conducted to assess the robustness of the results of the primary analysis and the secondary analysis of the proportion of normokalemic patients at the end of the 28-day randomized treatment study phase and during the 28-day randomized treatment study phase.

There is no planned interim analysis in this study.

Assuming an inter-subject standard deviation of 0.50, approximately 250 patients, (100 patients per active dose treatment arm and 50 patients for placebo control arm), will provide >90% power to detect a mean difference of 0.30 in mean 28-day randomized treatment phase Day 8-29, comparing each active dose (high to low) vs. placebo control using a two-sided t-test at a significance level of 5%. Assuming 90% of patients will be normokalemic after treatment in the open label initial phase (see Section 7.2), approximately 280 patients will be needed to enter the open-label initial phase.

TABLE OF CONTENTS

VERSIC	ON HISTORY	2
CLINIC	AL STUDY PROTOCOL SYNOPSIS	15
TABLE	OF CONTENTS	22
LIST OI	F ABBREVIATIONS AND DEFINITION OF TERMS	27
1.	INTRODUCTION	29
1.1	Background and rationale for conducting this study	29
1.2	Rationale for study design, doses and control groups	
1.3 1.3.1 1.3.2 1.3.3	Benefit/risk and ethical assessment Clinical benefits Clinical risks Clinical benefit-risk balance	34 34

Table 4	Volume of blood to be withdrawn from each patient: optional pre- screening and open-label initial phase	69
Table 5	Volume of blood to be withdrawn from each patient: 28-day randomized treatment study phase	70
Table 6	Confirmatory Testing Sequence	85

LIST OF FIGURES

Figure 1	Multivariable-adjusted mortality by serum potassium level in a cohort of 55,266 patients with eGFR <60 ml/min per 1.73 m2	
	during median follow up 2.76 years (Lou J et al 2016)	63
Figure 2	Forest plot of benefits (green) and risks (red) for ZS 10g and 15g	5
Figure 3	Study flow chart	;7
Figure 4	Flow chart based on the Potassium level, which will be measured by i-STAT	52

LIST OF APPENDICES

Appendix A	Additional Safety Information	97
Appendix B	Handling of Human Biological Samples	99
Appendix C	Guidance related to assessments and procedures during COVID-19 pandemic.	101

LIST OF ABBREVIATIONS AND DEFINITION OF TERMS

Abbreviation or special term	Explanation
ACE	Angiotensin-converting-enzyme
AE	Adverse event
ALP	Alkaline phosphatase
ALT	Alanine aminotransferase
ARBs	Angiotensin-receptor blockers
AST	Aspartate aminotransferase
AZ	AstraZeneca
AZRand	AZ global Randomization System
BP	Blood pressure
BUN	Blood Urea Nitrogen
CI	Confidence Interval
CKD	Chronic Kidney Disease
CRO	Clinical Research Organization
CSA	Clinical Study Agreement
CSR	Clinical Study Report
CTCAE	Common Terminology Criteria for Adverse Event
DAE	Discontinuation of Investigational Product due to Adverse Event
DM	Diabetes mellitus
DNA	Deoxyribonucleic acid
EC	Ethics Committee, synonymous to Institutional Review Board (IRB) and Independent Ethics Committee (IEC)
ECG	Electrocardiogram
eCRF	electronic Case Report Form
EOS	End of Study
FAS	Full Analysis Set
FAS-OLP	Full Analysis Set for the Open-Label Initial Phase
FAS-RTP	Full Analysis Set for the 28-day Randomized Treatment Study Phase
GCP	Good Clinical Practice
GFR	Glomerular Filtration Rate

The following abbreviations and special terms are used in this study Clinical Study Protocol.

Abbreviation or special term	Explanation
GGT	Gamma-glutamyl transferase
ICF	Informed Consent Form
ICH	International Conference on Harmonization
International Co-ordinating investigator	The Investigator co-ordinating the investigators and/or activities internationally
ITT	Intent-to-Treat
Hb	Haemoglobin
HCG	Human chorionic gonadotropin
HF	Heart Failure
IP	Investigational Product
IVRS	Interactive Voice Response System
IWRS	Interactive Web Response System
MedDRA	Medical Dictionary for Regulatory Activities
PGx	Pharmacogenetic research
PI	Principal Investigator
РО	Per Os
РР	Per Protocol
P-Renin	Plasma-Renin
qd	once daily
qod	every other day
RAAS	Renin-angiotensin-aldosterone system
RBC	Red Blood Cell
S-Aldo	Serum-Aldosterone
SAE	Serious adverse event
SAF	Safety Analysis Set
SAF-OLP	Safety Analysis Set for the Open-Label Initial Phase
SAF-RTP	Safety Analysis Set for the 28-day Randomized Treatment Study Phase
SAP	Statistical Analysis Plan
SARs	Suspected Adverse Reactions
S-Ca	Serum calcium
S-HCO3	Serum bicarbonate

Abbreviation or special term	Explanation
S-K	Serum potassium
S-Mg	Serum magnesium
S-Na	Serum sodium
S-PO4	Serum phosphate
SPS	Sodium Polystyrene Sulfonate
SST	Serum Separator Tube
tid	three times a day
VS	Vital Sign
WBC	White Blood Cell
WBDC	Web Based Data Capture
WHODrug	World health Organization Drug Dictionary
ZS	Sodium Zirconium Cyclosilicate (SZC)

1. INTRODUCTION

1.1 Background and rationale for conducting this study

Potassium is a ubiquitous ion, involved in numerous processes in the human body. It is the most abundant intracellular cation and is critically important for numerous physiological processes, including maintenance of cellular membrane potential, homeostasis of cell volume, and transmission of action potentials. The main dietary sources are vegetables (tomatoes and potatoes), fruit (oranges, bananas) and meat. The normal potassium values in serum (S-K) are between 3.5 and 5.0 mmol/L, with the kidney being the main regulator of potassium values. The renal elimination of potassium is passive (through the glomeruli) with active reabsorption in the proximal tubule and the ascending limb of the loop of Henle. There is active excretion of potassium in the distal tubules and the collecting duct, both of which processes are controlled by aldosterone.

Hyperkalemia develops when there is excessive production (oral intake, tissue breakdown) or insufficient elimination of potassium. Insufficient elimination, which is the most common cause of hyperkalemia, can be hormonal (as in aldosterone deficiency), pharmacologic (treatment with angiotensin-converting-enzyme [ACE] inhibitors or angiotensin-receptor blockers [ARBs]) or, most commonly, due to reduced kidney function. Increased extracellular potassium values result in depolarization of the membrane potential of cells. This depolarization opens some voltage-gated sodium channels, but not enough to generate an action potential. After a short period of time, the open sodium channels inactivate and become refractory, increasing the threshold to generate an action potential. This leads to impairment of the neuromuscular, cardiac, and gastrointestinal organ systems, and is responsible for the symptoms seen with hyperkalemia. Of

greatest concern is the effect on the cardiac system, where impairment of cardiac conduction can lead to fatal cardiac arrhythmias such as asystole or ventricular fibrillation. Because of the potential for fatal cardiac arrhythmias, hyperkalemia represents an acute metabolic emergency that must be immediately corrected.

The most common cause of hyperkalemia is renal insufficiency, and there is a close correlation between the degree of kidney failure and S-K values. In addition, a number of different commonly used drugs can cause hyperkalemia, such as ACE inhibitors, ARBs, potassiumsparing diuretics (e.g., amiloride, spironolactone), nonsteroidal anti-inflammatory drugs (e.g., ibuprofen, naproxen, celecoxib), heparin, and certain cytotoxic and antibiotic drugs (e.g., cyclosporin and trimethoprim). Finally, beta-receptor blocking agents, digoxin or succinylcholine are other well-known causes of hyperkalemia. In addition, advanced degrees of heart failure (HF), massive injuries, burns, or intravascular hemolysis cause hyperkalemia as can metabolic acidosis, most often as part of diabetic ketoacidosis.

Symptoms of hyperkalemia are non-specific and include malaise and muscle weakness or signs of cardiac arrhythmias, such as palpitations, bradycardia, or tachycardia. Often, however, the hyperkalemia is detected during routine screening blood tests for a medical disorder, or after complications have developed, such as cardiac arrhythmias or sudden death.

Diagnosis is established by S-K or plasma potassium measurements. Serum potassium values are most commonly used for diagnosis and to evaluate treatment response.

Treatment of hyperkalemia depends on the S-K values. In mild to moderate hyperkalemia acute treatment with a potassium-binding resin, combined with dietary advice (low potassium diet) and possibly modification of drug treatment (if treated with drugs causing hyperkalemia) will be standard of care. In severe hyperkalemia, or if arrhythmias are present, emergency lowering of potassium and close monitoring in a hospital setting are mandated.

- Sodium polystyrene sulfonate (sodium polystyrene sulfonate [SPS]; e.g., Kayexalate) is a resin that binds potassium in the intestine and increases fecal excretion, thereby reducing S-K values. However, as SPS has been shown to cause intestinal obstruction and potential rupture, diarrhea needs to be simultaneously induced, significantly reducing the palatability of the treatment. Even without the induction of diarrhea, a substantial proportion of patients complain of gastrointestinal symptoms, such as constipation, abdominal pain, cramping, distension, nausea, and vomiting. In addition, SPS is non-specific and also binds calcium and magnesium, thereby increasing the risk of inducing hypocalcemia and/or hypomagnesemia.
- Intravenous insulin (administered with or without glucose to prevent hypoglycemia) to shift potassium into the cells and away from the blood.
- Intravenous calcium gluconate or chloride decreases myocardial excitability and stabilizes the myocardium, reducing the risk for cardiac arrhythmias, but does not affect S-K.

• Severe cases not responding to other medical therapy may require dialysis.

Thus, the only pharmacologic therapy that increases elimination of potassium from the body is SPS. However, due to the need to induce diarrhea, SPS cannot be administered on a chronic basis. Even in the acute setting, the need to induce diarrhea, combined with inconsistent efficacy and a foul smell and taste, reduces the usefulness of SPS. Hence, there is a significant medical need for new and better treatment modalities for the acute as well as chronic treatment of hyperkalemia.

ZS-9 is a microporous zirconium silicate with a specific crystal geometry that confers a high, selective exchange capacity for potassium and ammonium ions. Sodium zirconium cyclosilicate (ZS) is a partially protonated form of ZS-9 that is being developed for the treatment of hyperkalemia.

ZS has been shown to bind potassium in the intestine of animals in exchange for hydrogen and sodium. The potassium-binding capacity of ZS has been shown *in vitro* to be approximately 10 times that of SPS in the presence of calcium and magnesium cations, which would represent a significant therapeutic advantage over SPS. *In vivo* studies in dogs and rats demonstrated significant dose-related reductions in the fractional excretion of urinary potassium up to 95% without any change in serum magnesium or calcium levels. Toxicology studies have shown ZS to be well tolerated at doses up to ~2.3-fold higher than the maximum three times a day ZS dose planned for registration or ~14-fold higher than the recommended starting once daily dose of 5 g per day. In addition, animal studies have demonstrated that ZS is not systemically absorbed, but exerts its effects locally in the gastrointestinal tract, significantly reducing the risk of any systemic toxicity.

As of September 2019, the clinical efficacy and safety of ZS in the treatment of hyperkalaemia has been assessed in 9 Phase 2/Phase 3 studies: 6 randomised, double blind, placebo controlled studies and 3 open label dose titration studies. In these studies, 2343 subjects with hyperkalaemia received at least 1 dose of ZS.

Clinical studies in subjects with hyperkalaemia consistently demonstrated that initial treatment with ZS 10 g tid for 24 h up to 72 h resulted in clinically meaningful S-K reduction with a majority of subjects achieving normokalaemia within 24 to 48 hours. Moreover, subjects with higher baseline S K levels had greater reductions in S K levels. Onset of efficacy was rapid with S-K reduction observed as early as 1 hour after dose intake.

After correction of hyperkalaemia, continued maintenance treatment for 28 days with ZS 5 g, 10 g, or 15 g qd resulted in continued effective control of S K within the normokalemic range. The proportion of subjects who remained normokalemic at the end of treatment with ZS 5 g, 10 g, and 15 g qd increased dose dependently (range: 71% to 85%) and was superior to placebo. In addition, long-term maintenance treatment of up to 12 months with ZS utilising a dose titration scheme with the starting dose of 5 g qd or 10 g qd, titrated to a maximum of 15 g qd or a minimum of 5 g qod was effective in maintaining normokalaemia in the majority of subjects.

A detailed description of the chemistry, pharmacology, efficacy and safety of ZS is provided in the Investigator's Brochure.

1.2 Rationale for study design, doses and control groups

This phase 3 study was intended to be included in applications for marketing authorization in the countries where the study is performed. ZS was approved in China for hyperkalemia based on overseas data at the end of 2019, now this is a post-approval commitment study for China.

A double-blind, placebo-controlled, randomized study represents the optimal design for obtaining unbiased estimates of treatment group differences for a new drug under development. Recognizing that all patients will receive active treatment during the open-label initial phase, combined with the fact that all patients will be monitored in the clinic for at least 4 hours after the initial dose of ZS, the level of hyperkalemia that could be included is not limited.

The randomized portion of the study (the 28-day randomized treatment study phase) is designed to assess whether extended administration of ZS maintains control of S-K values and to demonstrate that hyperkalemia recurs once ZS is withdrawn. Such design represents state-ofthe-art in demonstrating the need for ongoing longer-term treatment of a new drug under development. A 28-day randomized treatment study phase is selected as a compromise between ensuring a sufficiently long treatment period to demonstrate that ZS can maintain normokalemia over extended time, while not exposing patients with a potentially life-threatening condition to extended treatment with placebo. Eligibility for the open-label initial phase, eligibility for the 28-day randomized treatment study phase, and potassium-related stopping criteria are based on i-STAT measurements as these decisions need to be made in 'real-time' due to the risk of potentially life-threatening cardiac arrhythmias associated with severe hyperkalemia or hypokalemia. However, all endpoint analyses will be based on standardized S-K measurements analyzed at a central laboratory. For treatment decisions (i.e., S-K values on i-STAT < 3.5mmol/L), a second i-STAT sample will be taken 10 minutes after the initial abnormal sample to ensure that treatment is only changed once hypokalemia is confirmed. For a treatment decision to be made, both samples, taken 10 minutes apart, need to be below 3.5 mmol/L.

[figure not shown]
The design of this study is similar to the global ZS-004 study. In study ZS-004 (Kosiborod M et al 2014), ZS was highly effective in reducing S-K in patients with hyperkalemia, demonstrating statistically significant improvement from baseline in S-K with ZS 10 g TID over the first 48 hours of dosing. Patients who achieved normokalemia after receiving ZS 10 g TID in the Acute Phase were randomized to 28 days of placebo, ZS 5 g qd, ZS 10 g qd, or ZS 15 g qd dosing during the Maintenance Phase. ZS was effective in maintaining normokalemia (S-K between 3.5 mmol/L and 5.0 mmol/L, inclusive), meeting the predefined primary efficacy endpoint of mean S-K value during Maintenance Phase Study Days 8 to 29 at all 3 doses of ZS. Treatment with ZS was well tolerated in the patients recruited in ZS-004. The doses studied in this study were selected considering both efficacy and tolerability of the doses studies in ZS-004. Specific exclusion criteria ensure that appropriate patients, who are not at excess risk from treatment, will be enrolled. The multicenter design enhance the external validity, reproducibility, and generalizability of the results observed.

The patient selection criteria allows for the assessment of both efficacy and safety of ZS in a relevant population of patients with hyperkalemia. Since hyperkalemia affects both men and women, the inclusion criteria allows equal access to the protocol for both sexes. Exclusion criteria are developed based on consideration of safety concerns and to prevent enrollment of patients who are unsuitable for the study. In order to ensure the study population reflect 'real life', the exclusion criteria are not extensive, as the Sponsor want to ensure that the patient population enrolled is representative of the patient population receiving the drug post-approval. Hence, a large number of concomitant diseases and concomitant treatments are allowed, recognizing that many patients with hyperkalemia would also suffer from a range of concomitant diseases. This approach was further justified by the favorable safety and tolerability profile observed in Study ZS-003 and Study ZS-004, combined with the fact that ZS is not systemically absorbed.

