3.1 Inclusion criteria

Optional Pre-screening part of the study

For inclusion in the study patients should fulfil the following criteria:

- 1. Provision of informed consent (pre-screening consent) prior to any study specific procedures
- 2. Female and male patients aged ≥ 18 and ≤ 90 years

Main part of the study

Above inclusion criteria 2 is also applied to the Main part of the study. In addition, for inclusion in the study patients should fulfil the following criteria:

- 3. Provision of informed consent prior to any study specific procedures
- Two consecutive i-STAT potassium values, measured 60-minutes (± 10 minutes) apart, both ≥ 5.1 mmol/L and measured within 1 day of the first ZS dose on openlabel initial phase Day 1
- 5. Ability to have repeated blood draws or effective venous catheterization

6. Female patients must be 1 year post-menopausal, surgically sterile, or using an acceptable method of contraception (an acceptable method of contraception is defined as a barrier method in conjunction with a spermicide) for the duration of the study (from the time they sign consent) and for 3 months after the last dose of ZS/matching placebo to prevent pregnancy. In addition, oral contraceptives, approved contraceptive implant, long-term injectable contraception, intrauterine device, or tubal ligation are allowed. Oral contraception alone is not acceptable; additional barrier methods in conjunction with spermicide must be used.

Note: Whenever possible, all blood draws collected prior to meals should be collected prior to insulin/insulin analog treatment.

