4.3.1 Open-label initial phase Day 1 (Visit 3)

Patients will arrive in the morning, fasting (nothing by mouth except water for a minimum of 8 hours prior to potassium sample collection at the clinic).

The following assessment will be performed:

- Review and confirm the patient's eligibility for the study by assessing inclusion and exclusion criteria listed in Sections 3.1 and 3.2.
- Two potassium samples for assessment, using both i-STAT and the Central Laboratory, will be collected 60 minutes (± 10 min) apart.
- If either i-STAT potassium value is <5.1 mmol/L the patient will be declared a screen failure and withdrawn from the study.
- If both i-STAT values are ≥ 5.1 mmol/L the following samples will be collected:
 - A blood sample for standard assessment of hematology and clinical chemistry
 - Urine for standard assessment of urinalysis parameters including a pregnancy test if the patient is a woman of childbearing potential
- Obtain vital signs (pulse rate and blood pressure)
- Patient medical and surgical history including co-morbidities (over previous 6 months) will be obtained with the review of selection criteria
- Perform 12-lead Electrocardiogram (ECG)
- Perform a complete physical examination including weight, see Section 5.2.2;
- Review and record the concomitant medications and AEs/SAEs

Note: The above procedures should be performed within 1 day of the first administration of study drug and before any IP administration.

Patients who meet all inclusion/exclusion criteria will be entered into the trial and the following procedures will take place:

- The site will access the IVRS/IWRS and the system will assign the patient an openlabel initial phase IP kit
- The first doses of study IP will be administered as a slurry/suspension in water. The patient will be shown/instructed on how to mix and administer the IP
- 1 hour (± 15 min) after dose administration a blood potassium sample (i-STAT and Central Laboratory) will be collected, following which the patient is allowed to break the fast
- Two additional blood potassium samples (i-STAT and Central Laboratory) will then be taken at 2 and 4 hours (±15 min) after dose administration.

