3.2.1.1 Full analysis set in Open-label initial phase (FAS-OLP)

For the open-label initial phase (OLP), the full analysis set will include all subjects who received at least 1 dose of study medication in the open-label initial phase.

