3.3.1 General Study Level Definitions

3.3.1.1 Definition of Baseline Efficacy Baseline

For the OLP: The baseline Serum Potassium (S-K) will be established on the OLP Study Visit 3 (pre-dose) by taking the mean of 2 different S-K values.

For the RTP: The baseline S-K, S-Aldo and P-Renin will be established based on the last prerandomization measurement for S-K, S-Aldo and P-Renin, respectively, obtained during the OLP.

If baseline S-K C-lab values are missing, the i-STAT data will be used to replace them as described in Section 4.2.1.3. Subjects with missing values at baseline will be excluded from the relevant efficacy analysis.

Safety Baseline

Safety analyses will be performed separately for OLP and RTP. For change from baseline tabulations (laboratory measurements, vital signs, ECG and weight) the baseline will be defined as follows:

For OLP: Baseline will be the last non-missing measurement taken prior to first IP administration during OLP. If a measurement was taken on the date of first IP administration and no time is recorded, it is assumed that the measurement was taken pre-dose and will be considered a candidate for baseline.

For RTP: Same as OLP baseline, i.e. the last non-missing measurement taken prior to first IP administration during OLP.

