3.3.5 Handling of Missing Serum Potassium (S-K) Data

The S-K levels used for all analyses will be based on the central laboratory (c-lab) measurements. If the S-K c-lab data points are missing, the i-STAT data will be used to replace missing data by adjusting for the average paired difference between the c-lab and i-STAT levels collected at the same visit and with the same calibration method for the potassium assay. If the time difference between the SK c-lab and i-STAT measurements is greater than 15 minutes, the SK measure for that time point will be set as missing.

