4.2.2 Secondary Endpoints for OLP phase

4.2.2.1 Definition

The secondary efficacy endpoints for OLP phase will include the following:

- 1. Proportion of subjects who achieve normokalemia during the OLP at 24 hours (OLP Day 2) and at the end of the OLP. Each subject is classified into a responder or a non-responder category (i.e. a 0-1 type of response for subjects who achieve normokalemia or subjects who do not achieve normokalemia), with a subject being a responder if they have S-K between 3.5 and 5.0 mmol/L, inclusive. The following 7 time points during the OLP phase will be considered:
 - OLP Day 1, at 1, 2 and 4 hours post first dose
 - OLP Day 2, pre-dose and 1 hour post dose
 - o OLP Day 3, pre-dose
 - End of OLP

Note: not all subjects will have OLP Day 2, 1 hour post dose and OLP Day 3 pre-dose visit.

2. Exponential rate of change in S-K levels (blood) at 24 hours during OLP

- 3. Mean change (absolute and percent (%) change) from baseline in S-K levels at all measured time intervals post-dose during OLP listed above.
- 4. Time to normalization in S-K levels (normalization defined as first time S-K levels between 3.5-5.0 mmol/L, inclusive, are achieved) during OLP

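### Open-label normalisation is judged on central S-K with no condition on the central baseline, so patients already at 3.5-5.0 mmol/L before dosing can count as corrected

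*Protocol*

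**What the plan says.** **Entry (i-STAT).** Protocol section 3.1 requires "Two consecutive i-STAT potassium values, measured 60-minutes (± 10 minutes) apart, both ≥ 5.1 mmol/L", and section 4.3.1 enforces it: "If either i-STAT potassium value is <5.1 mmol/L the patient will be declared a screen failure and withdrawn from the study".

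**Endpoints (central laboratory).** Protocol section 1.2 states "However, all endpoint analyses will be based on standardized S-K measurements analyzed at a central laboratory". SAP section 3.3.5 agrees: "The S-K levels used for all analyses will be based on the central laboratory (c-lab) measurements". Adjusted i-STAT values only fill gaps where the central value is missing.

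**Baseline.** SAP section 3.3.1.1: "The baseline Serum Potassium (S-K) will be established on the OLP Study Visit 3 (pre-dose) by taking the mean of 2 different S-K values". Under that section a missing baseline removes a subject from the relevant analysis. A normal one does not.

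**Analysis set.** SAP section 3.2.1.1: "the full analysis set will include all subjects who received at least 1 dose of study medication in the open-label initial phase".

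**Responder.** SAP section 4.2.2.1 classifies each subject at each time point, "with a subject being a responder if they have S-K between 3.5 and 5.0 mmol/L, inclusive".

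**Time to normalisation.** The same section has "normalization defined as first time S-K levels between 3.5-5.0 mmol/L, inclusive, are achieved". Sections 4.2.2.2 and 4.2.2.4 run the clock from first dose, use all open-label S-K assessments, and report Kaplan-Meier estimates at 1, 2, 4, 24 and 48 hours.

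**The concern.** Hyperkalaemia is established with one method and its correction is judged with another. The plan itself expects the two to differ, because it prescribes a paired-difference adjustment when an i-STAT value stands in for a central one. SAP section 3.3.7 (notes to Table 3) defines hyperkalaemia as S-K of 5.1 or more. A patient with a central baseline of 4.9 is not hyperkalaemic on that scale, yet needs no change in potassium to be a responder, and enters the Kaplan-Meier risk set already in the event state.

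The proportion achieving normokalaemia is the stated open-label objective (protocol section 2.2), and time to normalisation is its speed measure. This phase has no control arm, so the credit does not cancel. SAP section 4.2.2.5 lists no sensitivity analysis, and section 4.2.2.6 covers only disallowed medication and the 48-hour rate of change.

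**Working it through.** **1. The plan's own figure.** Protocol section 8.2 assumes 90% are normokalaemic after the open-label phase: 250/0.90 = 278, against a stated 280. This reproduces and is not in dispute. I use 280 only as a denominator.

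**2. Reading the rules together.** Entry: both i-STAT values at least 5.1. Set: everyone dosed. Event: central S-K of 3.5-5.0 at a post-dose time. No rule in SAP sections 3.2.1.1, 3.3.1.1 or 4.2.2.1 to 4.2.2.6 excludes, separates or left-censors a subject whose central baseline is already 3.5-5.0.

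**3. How many patients.** The documents give neither the sign nor the size of the i-STAT/central difference, so this step is assumption only. Assumed: potassium in the screened population with mean 5.2, between-patient SD 0.45 and day-to-day SD 0.25; i-STAT error SD 0.12-0.20; central error SD 0.10-0.15; all values reported to 0.1; baseline as the mean of two central values. Simulated among patients with both i-STAT values at least 5.1:

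| Central minus i-STAT | Central baseline 5.0 or less | Of 280 | Of these, in range at 1 h with no drug effect |
|---|---|---|---|
| -0.2 | 15-17% | 43-48 | 66-78% |
| -0.1 | 7-9% | 20-24 | 54-72% |
| 0 | 2-4% | 6-10 | 42-64% |
| +0.1 | 0.4-1.3% | 1-4 | 29-56% |
| +0.2 | 0-0.4% | 0-1 | 19-49% |

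A second set of assumptions (source mean 5.2, 5.5 or 5.8; between-patient SD 0.4; within-patient SD 0.1; i-STAT error 0.1-0.2) gives 0 to about 11%, or 0 to about 32 of 280. Reporting both assays to 0.1, with source mean 5.2 and central error 0.1, lifts the top of that set to about 18%. Hence an upper end of roughly 10-20%. In the second set, if S-K falls by an assumed 0.1 by 1 hour, 83-91% of the baseline-normal patients are in range then, wherever their share is at least 1%.

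**4. Effect on the responder proportions.** Let R be the proportion in all dosed patients, q the share already normal, and r the response rate among those. The rate in patients above 5.0 at baseline is (R - q x r)/(1 - q). Take r = 0.95 (assumed). For R, use the ZS-004 rates in protocol section 1.3.1, 77% at 24 hours and 86% at 48 hours, as examples only.

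- q = 0.03: (0.77 - 0.0285)/0.97 = 76.4%; (0.86 - 0.0285)/0.97 = 85.7%
- q = 0.05: (0.77 - 0.0475)/0.95 = 76.1%; (0.86 - 0.0475)/0.95 = 85.5%
- q = 0.10: (0.77 - 0.095)/0.90 = 75.0%; (0.86 - 0.095)/0.90 = 85.0%
- q = 0.20: (0.77 - 0.19)/0.80 = 72.5%; (0.86 - 0.19)/0.80 = 83.75%

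**5. Effect on the early Kaplan-Meier curve.** Suppose the curve reads 50% at some early hour and q = 0.10. If all baseline-normal patients have been counted by then, the figure for patients above 5.0 at baseline is (0.50 - 0.10)/0.90 = 44%. If only 60% have, it is (0.50 - 0.06)/0.90 = 49%. At q = 0.03 the same two cases give (0.50 - 0.03)/0.97 = 48% and (0.50 - 0.018)/0.97 = 50%.

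**The case against.** **The population is defined on i-STAT by design.** Entry decisions must be made in real time, the objectives define hyperkalaemic patients by i-STAT, and efficacy follows the full analysis set. This stands as a reason to keep the full-set analysis. It does not make the full-set figure a measure of how many were corrected on the endpoint's own scale.

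**The number may already be visible.** SAP section 4.2.2.4 lists baseline first among its S-K summaries and then tabulates normokalaemia at the time points listed. Read literally, that gives a baseline row, although the list in section 4.2.2.1 omits baseline. Even so, such a row would not correct the proportions or the curve.

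**The effect is small and nothing confirmatory rests on it.** This stands. At 86% with n = 280 the 95% half-width is 1.96 x sqrt(0.86 x 0.14/280) = 4.1 points, against a shift of about 1 point at a 10% share. Both endpoints are descriptive. The only open-label test in the confirmatory sequence is the mean change in S-K.

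**Stronger readings that the documents do not support.**
- A reader might infer that many patients are affected. No figure in the documents says so, and the share could be near zero.
- A reader might take the already-normal share as a floor under the 1-hour rate. It is not: with no drug effect, only about 42-78% of these patients are in range at 1 hour where the share is 2% or more.
- A reader might suppose that early events are mostly spurious because little true normalisation occurs in the first hours. Protocol section 1.3.1 reports a median of 2.2 hours in ZS-004, which contradicts that.

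**Conclusion.** The gap is in the text and holds whatever the assay difference: followed exactly, the plan can credit ZS with correcting patients who had nothing to correct on the endpoint's scale. Its size cannot be derived from the documents. Under the assumptions above it runs from near 0% to roughly 10-20% of dosed patients, and about 2-4% at zero offset. The 24-hour and end-of-phase proportions then move by a fraction of a point to about 2 points for shares up to 10%, and by up to 4.5 points at 20%. The early Kaplan-Meier estimates, on which any statement about speed rests, move more.

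A reader might go on to doubt the main trial result. The documents do not support that: neither endpoint is in the testing hierarchy of SAP section 3.3.7, and the randomised comparison of each dose with placebo does not use them. The point is worth acting on because it bears on how many patients were corrected and how fast, and the data to settle it are already collected.

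**What to change.** In SAP sections 4.2.2.4 and 4.2.2.6:

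- Keep the analysis in all of FAS-OLP.
- Report the number and percentage with open-label baseline S-K (central, or adjusted i-STAT where missing) of 3.5-5.0 mmol/L.
- Pre-specify the responder proportions at 24 hours and end of phase, and time to normalisation, in FAS-OLP subjects with open-label baseline S-K above 5.0. Show them beside the full-set figures and use them for any statement about correction of hyperkalaemia or its speed.

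The condition should be above 5.0 rather than at least 5.1. Baseline is a mean of two values, so 5.05 can occur, and such a subject would fall into neither group. Under the first set of assumptions at zero offset that gap holds about 2% of patients.

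Cost: one extra analysis, a slightly smaller denominator and slightly less favourable figures. Conditioning on a pre-dose value in a single-arm phase disturbs no randomisation. It is not a complete cure: some subjects just above 5.0 will still cross the cut-off through assay noise, and selecting on the outcome assay brings some regression to the mean. If the number already normal proves close to zero, the table shows that the full-set figures can be read as they stand.
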